## IV. ADVERSE EVENTS

### A. Definition of an Adverse Event

**Adverse event.** An adverse event (AE) in SARP shall be considered any detrimental change in the patient's condition related to an asthma exacerbation or to a SARP procedure.

**Anticipated adverse event.** Anticipated adverse events are defined for each of the protocol procedures in the sections specifically written for those procedures (see below).

**Unanticipated adverse event.** Any adverse event that results in risk or harm to the subject or others that differs from the known, predicted possible effects of the research protocol. An unanticipated adverse event is one that varies in nature, intensity, or frequency from information in the informed consent document.

**Serious adverse event.** Any event that results in death, inpatient hospitalization or prolongation

of existing hospitalization, a persistent or significant disability or incapacity, or a congenital anomaly or birth defect. Important medical events that may not result in death, be life-threatening, or require hospitalization may be considered a serious adverse event when, based upon appropriate medical judgment, they may jeopardize the patient or subject and may require medical or surgical intervention to prevent one of the outcomes listed above.

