## **B. Monitoring of adverse events related to the study**

The occurrence of an AE may come to the attention of study personnel during study visits or telephone interviews or by a patient presenting for medical care. The following AEs are expected from participation in the study.

**Blood draw:** Subjects may experience some lightheadedness or nausea while having blood drawn. There is a risk of bruising at the site where the needle enters the skin and a remote risk of infection.

**Spirometry and maximum bronchodilation:** Subjects may experience shortness of breath while doing spirometry, and very rarely, syncope. Temporary wheezing and chest tightness infrequently (5% of the time) occur. Following the bronchodilator, there is likely (>25% chance) to be a transient increase in heart rate and tremor. Adults taking 4 puffs of ipratropium (Atrovent® HFA) for this test may experience headache, dry mouth, nausea, bronchitis, and shortness of breath. These side effects were reported in patients with COPD who took ipratropium for 12-weeks [Boehringer Ingelheim Pharmaceuticals, Inc. USPI, Revised 8/2012]. Since participants will only take ipratropium once, the likelihood of these side effects is much less. These side-effects are non-life threatening and are short-lived.

**Methacholine Challenge:** Subjects may experience shortness of breath, coughing, lightheadedness and dizziness. In rare cases, some patients have experienced a severe asthma attack or a reaction to the methacholine. Subjects with a pre-diluent FEV1 of >50% predicted (>70% in children aged 6 to 17 years) and at least one liter will undergo the methacholine testing if they do not have a historical methacholine from a previous NIH trial (CARE, AsthmaNet, SARP I or II, or ACRN) and a physician will be available during the challenge. Subjects will not be discharged until their FEV1 is within 10% of their pre-diluent FEV1.

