**Sputum Induction:** Subjects may experience a salty after taste in the mouth, coughing, a feeling of needing to swallow, a sore throat, shortness of breath, wheezing, chest tightness, lightheadedness, nausea or headache. In rare cases, some patients have had a severe asthma attack or a reaction to the salty water that they breathe in. Bronchodilator treatment will be available if this occurs. The following safety procedures will be followed for the sputum induction procedure; only subjects (aged 12 and above) with a post bronchodilator FEV1 of >50% predicted (>70% in children aged 12 to 17 years) will undergo sputum induction, a physician will be available during the challenge; study staff will calculate and record the peak flow and FEV1 value that equals both a 10% and 20% fall in lung function based upon the recorded post-bronchodilator peak flow and FEV1 values and subjects will not be discharged until their FEV1 is within 10% of their post bronchodilator FEV1.

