**Corticosteroid (triamcinolone acetonide) administration:** Severe triamcinolone injection side effects can include signs of an allergic reaction including hives; difficulty breathing; swelling of face, lips, tongue, or throat; thinning of bone, which could lead to fractures. Other side effects include: fast, slow, or uneven heart rate; feeling short of breath, even with mild exertion; swelling, rapid weight gain; increased blood pressure (severe headache, blurred vision, trouble concentrating, chest pain, numbness, seizure); problems with vision; eye swelling, redness, discomfort, or drainage (may be signs of infection); severe depression, changes in mood or behavior; seizure (convulsions); or muscle pain, tenderness, or weakness. Less serious side effects may include: nausea, bloating, appetite changes; stomach or side pain; headache, sleep problems (insomnia); acne, scaling, or other skin changes; a wound that is slow to heal; thinning hair; bruising or swelling; sweating more than usual; or irregular menstrual periods and pain and redness at the injection site. The latter side effects are minimized by deep injection into the gluteal muscle thus all triamcinolone acetonide injections will be administered by experienced, medically licensed personnel. Triamcinolone taken during pregnancy may expose the fetus to unknown risks, including the possibility of birth defects. Females of child bearing potential must use a medically acceptable method of birth control from the time of enrollment and continuing until 12 weeks following the triamcinolone injection. Subjects receiving triamcinolone acetonide will undergo a thorough history and physical examination and will be educated about signs of potential complications and will have 24-hour access to an on-call physician. Participants will also undergo a scheduled comprehensive evaluation shortly after the triamcinolone acetonide is administered. Despite rare risks, triamcinolone acetonide injection is thought to be generally safe, but there may be risks, discomforts, or side effects that are not yet known.

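### The serious adverse event definition omits life-threatening events from its automatic criteria, although its next sentence names them as if they were listed

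*Combined protocol and SAP*

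**What the plan says.** Section IV.A of the protocol defines a serious adverse event in two sentences.

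The first gives the outcomes that make an event serious without further judgment. It begins "Any event that results in death, inpatient hospitalization or prolongation" and, after a page break, continues "of existing hospitalization, a persistent or significant disability or incapacity, or a congenital anomaly or birth defect".

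The second adds a clause for important medical events: "Important medical events that may not result in death, be life-threatening, or require hospitalization may be considered a serious adverse event when", and the condition follows: "based upon appropriate medical judgment, they may jeopardize the patient or subject and may require medical or surgical intervention". The intervention must be aimed at preventing one of the outcomes in the first sentence.

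Section IV.B lists the reactions expected from study procedures. For methacholine: "In rare cases, some patients have experienced a severe asthma attack or a reaction to the methacholine". For sputum induction: "In rare cases, some patients have had a severe asthma attack or a reaction to the salty water that they breathe in". For the triamcinolone injection, the severe side effects include "signs of an allergic reaction including hives; difficulty breathing; swelling of face, lips, tongue, or throat".

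Section V.B attaches duties to the SAE label. A supplemental form is required, with one exception for unanticipated, non-fatal, unrelated events. Anticipated SAEs, and unanticipated ones that are at least possibly related, go to the Data Coordinating Center (DCC) and the local IRB within 3 business days; deaths go within 24 hours. The DCC passes SAE reports to the DSMB and NHLBI within 48 hours of receipt.

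**The concern.** The two sentences of the definition do not fit together. The second sets life-threatening between death and hospitalization, both of which the first sentence lists, but the first sentence does not list life-threatening itself. A reader of the second sentence would assume that the criterion is there.

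The gap matters for one kind of event: a reaction that threatens life, is treated successfully, and leads to no admission, lasting disability or death. The protocol foresees severe asthma attacks during two of its procedures and allergic reactions with airway signs after the injection. It also requires a physician to be available during both challenges, and it holds subjects until their FEV1 has recovered. A severe reaction that is resolved on site is therefore a realistic case.

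For such an event, the label decides whether expedited reporting is owed. If the label depends on discretion, the seven clinical centers can classify the same reaction differently, and the count of SAEs given to the DSMB is not comparable between centers.

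**Working it through.** No arithmetic applies, and the plan states no figure to reproduce. The check sets the two sentences side by side and then follows one event through the reporting rules.

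**Step 1. Criterion by criterion (Section IV.A).**

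| Criterion | In the first sentence (automatic)? | Named in the second sentence? |
|---|---|---|
| Death | Yes | Yes |
| Life-threatening | **No** | **Yes** |
| Hospitalization | Yes | Yes |
| Longer hospital stay | Yes | No |
| Disability or incapacity | Yes | No |
| Congenital anomaly or birth defect | Yes | No |

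Of the three criteria named in the second sentence, two are on the automatic list and one is not.

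**Step 2. Is the omission an artefact of text extraction?** It does not appear to be. The first sentence is split by a page break, but its two parts join grammatically with nothing missing between them.

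**Step 3. Does another section supply the criterion?** None does. The only other use of the term is in Section IV.B, which calls the bronchodilator side effects not life-threatening. Section V.B gives a special timeline only to deaths.

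**Step 4. Follow one event.** Take a severe, life-threatening asthma attack during sputum induction, reversed on site, with no admission and no lasting harm.

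- Automatic list: no criterion is met.
- Important-medical-event clause: it can be met on medical judgment, but the wording is permissive, so leaving the event unlabelled also complies.
- If labelled an SAE: the reaction is one that Section IV.B anticipates, so Section V.B requires the supplemental form, reporting within 3 business days, and forwarding within 48 hours. Because it happens at a visit, the exemption in Section V.B for asthma-related SAEs more than 30 days after the latest visit does not apply.
- If not labelled an SAE: Section V.B still requires an adverse event form, plus an Additional Treatment form sent to the DCC if treatment was needed during or just after the procedure. The event also enters the DCC's monthly report to the Steering Committee and the similar report for the DSMB's bi-monthly meetings. Section V.A adds a report within three working days to the DCC, Steering Committee, NHLBI and DSMB, but only if a procedure is suspended.

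**Step 5. The difference.** Both branches record the event. They differ in the label and in the assured 3-business-day and 48-hour steps.

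**The case against.** The strongest reply is that the important-medical-event clause already catches these events. Its opening can be read as covering events that might or might not be life-threatening, rather than only those that are not. Its test is whether intervention may be needed to prevent a listed outcome. Death is a listed outcome, so a life-threatening reaction reversed on site meets the test. This reading is sound. A reader might infer that the clause shuts life-threatening events out altogether, and the documents do not support that. The clause still only permits the label, however; it does not require it.

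A second reply is that nothing goes undetected. That stands in full: the forms and periodic reports in Section V.B, and the suspension rule in Section V.A, apply whatever the label. A reader might infer that such reactions would be lost or hidden from the DSMB, and that would be wrong. Only timing and classification are at stake.

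Third, deciding that an event is life-threatening is itself a judgment, so the fix does not remove discretion. That is true. It does make the label mandatory once that judgment has been made.

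Fourth, the affected set is limited. Asthma-related SAEs more than 30 days after a visit go to summary reporting in any case. Methacholine challenge and the injection belong to the characterization visits, and the text is version 12.0 of October 2019, so much of that exposure may be past. The documents do not say how much. Section III.D still schedules sputum induction at Visit 7 in the extension. The documents describe the severe attacks as rare, and they do not say that these reactions are especially likely to be life-threatening.

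Finally, the Manual of Procedures and the SAE form may carry the missing criterion. They were not available, and this cannot be excluded.

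**Conclusion.** The point holds in a limited form. The automatic SAE criteria in Section IV.A omit life-threatening events, the next sentence is worded as if they were included, and no other section fills the gap. A life-threatening reaction that resolves without admission or another listed outcome is therefore an SAE only at someone's discretion, and the expedited reporting in Section V.B is not assured for it.

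The size cannot be estimated: the documents give no rate for such reactions beyond calling the severe attacks rare. No hypothesis or planned analysis is affected. The consequence is uneven classification between centers and, for some events, slower notice to the DCC, IRB, DSMB and NHLBI.

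The conclusion assumes that the protocol text governs and that the SAE form and Manual of Procedures do not already add the criterion. If they do, what remains is a mismatch between documents that should still be corrected.

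**What to change.** Reconcile the two sentences in Section IV.A by adding *is life-threatening* to the outcomes listed in the first. Keep the important-medical-event clause as it stands, since it serves a different purpose. Then check that the SAE form, the Manual of Procedures and the reporting rules in Section V.B agree with the amended definition.

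The cost is a few words in the protocol, a matching edit to the form if it lacks the criterion, and at most a few more expedited reports. No study procedure changes.

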## **B. Monitoring of adverse events related to the study**

The occurrence of an AE may come to the attention of study personnel during study visits or telephone interviews or by a patient presenting for medical care. The following AEs are expected from participation in the study.

**Blood draw:** Subjects may experience some lightheadedness or nausea while having blood drawn. There is a risk of bruising at the site where the needle enters the skin and a remote risk of infection.

**Spirometry and maximum bronchodilation:** Subjects may experience shortness of breath while doing spirometry, and very rarely, syncope. Temporary wheezing and chest tightness infrequently (5% of the time) occur. Following the bronchodilator, there is likely (>25% chance) to be a transient increase in heart rate and tremor. Adults taking 4 puffs of ipratropium (Atrovent® HFA) for this test may experience headache, dry mouth, nausea, bronchitis, and shortness of breath. These side effects were reported in patients with COPD who took ipratropium for 12-weeks [Boehringer Ingelheim Pharmaceuticals, Inc. USPI, Revised 8/2012]. Since participants will only take ipratropium once, the likelihood of these side effects is much less. These side-effects are non-life threatening and are short-lived.

**Methacholine Challenge:** Subjects may experience shortness of breath, coughing, lightheadedness and dizziness. In rare cases, some patients have experienced a severe asthma attack or a reaction to the methacholine. Subjects with a pre-diluent FEV1 of >50% predicted (>70% in children aged 6 to 17 years) and at least one liter will undergo the methacholine testing if they do not have a historical methacholine from a previous NIH trial (CARE, AsthmaNet, SARP I or II, or ACRN) and a physician will be available during the challenge. Subjects will not be discharged until their FEV1 is within 10% of their pre-diluent FEV1.

**Sputum Induction:** Subjects may experience a salty after taste in the mouth, coughing, a feeling of needing to swallow, a sore throat, shortness of breath, wheezing, chest tightness, lightheadedness, nausea or headache. In rare cases, some patients have had a severe asthma attack or a reaction to the salty water that they breathe in. Bronchodilator treatment will be available if this occurs. The following safety procedures will be followed for the sputum induction procedure; only subjects (aged 12 and above) with a post bronchodilator FEV1 of >50% predicted (>70% in children aged 12 to 17 years) will undergo sputum induction, a physician will be available during the challenge; study staff will calculate and record the peak flow and FEV1 value that equals both a 10% and 20% fall in lung function based upon the recorded post-bronchodilator peak flow and FEV1 values and subjects will not be discharged until their FEV1 is within 10% of their post bronchodilator FEV1.

**Corticosteroid (triamcinolone acetonide) administration:** Severe triamcinolone injection side effects can include signs of an allergic reaction including hives; difficulty breathing; swelling of face, lips, tongue, or throat; thinning of bone, which could lead to fractures. Other side effects include: fast, slow, or uneven heart rate; feeling short of breath, even with mild exertion; swelling, rapid weight gain; increased blood pressure (severe headache, blurred vision, trouble concentrating, chest pain, numbness, seizure); problems with vision; eye swelling, redness, discomfort, or drainage (may be signs of infection); severe depression, changes in mood or behavior; seizure (convulsions); or muscle pain, tenderness, or weakness. Less serious side effects may include: nausea, bloating, appetite changes; stomach or side pain; headache, sleep problems (insomnia); acne, scaling, or other skin changes; a wound that is slow to heal; thinning hair; bruising or swelling; sweating more than usual; or irregular menstrual periods and pain and redness at the injection site. The latter side effects are minimized by deep injection into the gluteal muscle thus all triamcinolone acetonide injections will be administered by experienced, medically licensed personnel. Triamcinolone taken during pregnancy may expose the fetus to unknown risks, including the possibility of birth defects. Females of child bearing potential must use a medically acceptable method of birth control from the time of enrollment and continuing until 12 weeks following the triamcinolone injection. Subjects receiving triamcinolone acetonide will undergo a thorough history and physical examination and will be educated about signs of potential complications and will have 24-hour access to an on-call physician. Participants will also undergo a scheduled comprehensive evaluation shortly after the triamcinolone acetonide is administered. Despite rare risks, triamcinolone acetonide injection is thought to be generally safe, but there may be risks, discomforts, or side effects that are not yet known.

**Withholding medication:** After consenting, subjects will be asked to hold certain medications prior to each visit for the purpose of lung function testing. Subjects may experience an increase in their asthma symptoms from holding their daily medications. If subjects are unable to hold their medications, they are instructed to take the medication as needed and to call the study staff. This will also be documented and the subject will proceed with the scheduled procedure.

#### **C. Adverse events unrelated to asthma**

Adverse events due to concurrent illnesses other than asthma may be grounds for withdrawal if the illness is considered significant by the study investigator or if the patient is no longer able to effectively participate in the study. Subjects experiencing minor illnesses may continue in the study if the nature, severity, and duration of the illness are recorded. Examples of minor illnesses include gastroenteritis and skin disorders such as atopic dermatitis. Medications are allowed for treatment of these conditions.

Documentation of an adverse event unrelated to asthma, but leading to study withdrawal will be recorded on an Adverse Event Report Form and will include a description of the illness and the date the illness occurred.

#### **D. Risk-benefit ratio**

It is the belief of the investigators involved in this research that risks of the tests and procedures SARP III Longitudinal Protocol 21 V12.0 10/16/2019

associated with this study are justifiable given the knowledge to be gained. As previously mentioned, there is a paucity of data regarding severe asthma; as a result, these patients have the highest rates of morbidity and mortality. Therefore, the investigators believe that the benefits of this proposed study are sufficiently great enough to justify the approach.

Participants in this study may personally benefit from the clinical evaluation by an asthma physician specialist, close monitoring of their asthma, the education about asthma action plans, and general evaluation of their condition, particularly in a longitudinal design with follow up in and around the time of exacerbations. Some participants and families of children with asthma achieve psychological benefit from involvement in an important national research study and from interaction with the study staff. There is a possibility that the information obtained from participation in this study or treatments used will also directly benefit the participating subjects and their families. All research procedures will be completed free of charge to the research participants and their families. All research data collected for a subject will be available for that subject to review, in accordance with IRB policies. It is also possible that the knowledge obtained from this study may assist in the creation of novel asthma therapies in the future.

## **V. DATA MONITORING RATIONALE**

The quality of statistical evaluation of the outcome(s) of any study depends on the quality of the data collected during the study as much as it does on the appropriate statistical methods. If data are collected haphazardly, if assay results are not reproducible, or if data elements are often missing or un-interpretable, reasonable statistical inference is impossible.

The use of the SARP Manual of Procedures will provide the basis for consistent and reproducible results. The principal investigator at each clinical site will be responsible for assuring that the project staff members comply with the procedures outlined in the Manual of Procedures. The manual consists of a section to cover each component of the study from the initial screening visit to the final statistical evaluation of the data. A copy of the section(s) appropriate to each of the several sites handling subjects, biological samples, and data will be available at that site. A master copy will be available at the password-protected web site.

Each laboratory will be responsible for the reliability and validity of its data and will be asked to provide a copy of its control procedures for review by the Steering Committee.

The monthly accrual and expectations report provided to the Steering Committee will alert the PIs and their clinical teams to any problems in the rate of accrual and will prompt the clinical coordinators to follow up where the receipt of specimens is not recorded by the expected dates.

Data-integrity checks are programmed into the data management system, which flags exceptions to the quality control criteria. The DCC programs flag situations that indicate any potential problems with data interpretability, integrity, or a potential lack of compliance to the Manual of Procedures. The project is reviewed daily for the need for corrective action and this information is given to the centers on a daily basis, if needed. These actions taken by the DCC are reviewed by the Steering Committee at its monthly meetings. The Steering Committee will decide upon any corrective action that needs to be taken to ensure subject safety or data

integrity at its monthly meetings. The DSMB will also make recommendations about action after its review of the data.

